### 9.13.3 Tracking of Emergency Department Visits and Hospitalizations

For the DSMB reports prepared by [name] every 6 months, [name] will query the relevant EMR to extract data (type of medical visit and diagnostic codes) to be stored in an Excel file. [name] will report the total number of emergency department visits and hospitalizations among randomized participants in the DSMB reports. If evidence of treatment group imbalance emerges, further investigation by [name] will be initiated (e.g., examining reasons for the visits), and the results will be reported to the DSMB for their consideration.

### 9.13.4 Methods for Monitoring the Quality and Consistency of Data Collection

We will use our IU REDCap assessment databases to ensure the collection of high-quality data in a consistent fashion over time. These databases will serve as both the operations manual and the data collection instrument for study contacts. Specifically, each database will include step-by-step instructions (e.g., from the scheduling call to the closing of a visit) with a box to be checked by the team member when each step is completed. All interview questions and questionnaire items will be embedded in the databases, along with radio buttons, checklists, drop-down menus, or open fields to capture participant responses. There will be open fields to capture height, weight, and vital signs. Instructions for the electronic health record chart reviews and the corresponding data fields will also be embedded to capture relevant data (e.g., concomitant medications and insomnia care received outside the trial). Data quality (e.g., % missingness) will be assessed every 6 months before DSMB meetings, and data quality metrics will be reported to the DSMB every 6 months in [name] DSMB report.

### 9.13.5 Policies and Methods for Ensuring Blinding of Study Results

To ensure unbiased results, all outcomes assessors will be blinded to treatment group assignment, and all patients will be blinded to study hypotheses until the proposed trial is complete. Drs. [name] and [name] and the study personnel involved in treatment delivery (SHUTi vs. sleep education/hygiene) will not be blinded by necessity. [name] and [name] will have the master randomization list but will not share it with the blinded co-investigators and laboratory personnel performing the endpoint inflammation assays (Drs. [name] and [name]). At the Entry Visit, randomization will occur at the end of the session after all data collection for that visit is complete.

### 9.13.6 Data Confidentiality and Subject Privacy

All research material will be kept strictly confidential. All investigators and study personnel have completed or will complete the Collaborative Institutional Training Initiative (CITI) courses in Human Subjects Research and Good Clinical Practice and will make every effort to ensure confidentiality. All electronic and hard copy data will be identified using only the unique participant identification number assigned when each patient is enrolled (participant identifying information will not be included). All electronic data will be saved on password-protected and encrypted computers and secure servers, and all hard copy data will be stored in secure and locked file cabinets. The key linking participant names with the participant identification numbers will be

kept in a separate secure and locked file cabinet. Data will be analyzed and reported as an aggregate, with no individual identifying information.

To protect participant privacy, all in-person data collection will be conducted in private rooms at the Infectious Diseases Research Clinic. In addition, all study phone calls will be conducted from private rooms in [name] Behavioral Medicine Laboratory. No identifying information will be entered into SHUTi. Instead, participants will log on using their participant identification number and a password they create. Finally, participants will be instructed to complete study calls and SHUTi sessions in private rooms or areas in their homes or other locations they choose.

## 10.0 HUMAN PARTICIPANTS RESEARCH AND PROTECTION

### 10.1 General Considerations/Investigator Training

The Human Participants Research outlined in this proposal meets the definition of a Phase II clinical trial for the purpose of identifying biological and physiological mechanisms of human disease (not for identifying the superiority of one agent over the other). Although the NIH does not require a formal Data and Safety Monitoring Board, we will still employ one with an independent monitor as described below. This trial will be posted on ClinicalTrials.gov and updated regularly as needed for protocol updates and results. All Indiana University personnel involved with this application have successfully completed the training and examination involved with the Collaborative Institutional Training Initiative Course.

### 10.2 Risks to the Participants

#### 10.2.1 Human Participants Involvement and Characteristics

- A total of 50 HIV-positive participants will be recruited to participate in this pilot trial investigating the efficacy of internet cognitive behavioral therapy for insomnia using the SHUTi computer program to reduce systemic inflammation and monocyte activation.
  - Participants must be at least 18 years of age (no upper age limit), have documented HIV infection, have a screening HIV-1 RNA level <75 copies/mL while on ART for at least six months, and have insomnia disorder per the Structured Clinical Interview for DSM-5 Sleep Disorders.
  - The chief exclusion criteria include if they have another sleep disorder diagnosis (e.g. sleep apnea); have a schedule requiring a bedtime earlier than 8:00pm or later than 2:00am or arising time earlier than 4:00am or later than 10:00am (thus preventing adoption of SHUTi); have any other pro-inflammatory condition (e.g. autoimmune diseases); malignancy requiring treatment within 6 months of screening; are receiving systemic daily anti-inflammatories; have a history of bipolar or psychotic disorder; or are currently pregnant or breastfeeding.
  - Potential participants will be recruited from the Ryan White HIV outpatient clinics of Eskenazi Health Hospital and Indiana University Health Methodist Hospital.

#### 10.2.2 Sources of Materials

- All data for this study will be obtained only after verbal consent is provided during the Screening process and after written, informed consent is provided by each participant for the formal randomized, clinical trial portion of the study. Existing medical records will be reviewed for demographics, medical diagnoses, and medications. Blood samples will be obtained for testing of HIV-1 RNA levels, CD4 cell counts, and inflammation biomarkers. Urine samples will be obtained

for pregnancy testing. Plasma will be obtained and stored for future studies of interest. Questionnaires to assess insomnia, depression, tobacco and alcohol use, anxiety, medication adherence, physical activity, and fatigue will also be implemented.

- Results from pertinent medical records and procedures performed for these studies, as outlined above, will be recorded on the human participants involved in the projects in this application.
- Data will be stored in a password-protected computerized database via REDCap that will include only the participants' study identification number (names and other identifiable information will not be included). Therefore, the SID# will be the only link to the participant. Only the principal investigators, co-investigators, and research personnel who will directly obtain the necessary data will have access to the participant identities. All data obtained for this study will be obtained only after written, informed consent is provided by each participant.
- Records will be reviewed manually. Urine specimens will be obtained via standard clean-catch technique. Blood specimens will be obtained via peripheral venipuncture. Questionnaires will be completed in private settings. These data will be collected solely for the purpose of the proposed research projects.

#### 10.2.3 Potential Risks

- There are minimal risks to the participants enrolled in the proposed research. The first is the potential loss of participant confidentiality. The second consists of the risks associated with blood drawing/needle sticks, which include pain, bruising, infection, and phlebitis. The amounts of blood to be drawn at screening and at each main study visit are 5 cc (one teaspoon) and 18 cc (1-2 tablespoons), respectively. The total amount of blood to be obtained over the 24 week study period would be approximately 60 cc (4 tablespoons), which is well within the accepted standards for blood donation over a 6 month period. There are no known risks related to the implementation of the SHUTi cognitive behavioral therapy program in the Intervention Group or of the sleep education/hygiene program in the Active Control/Comparator group. Participants may also feel unease in completing the questionnaires.
- The principal alternative to these procedures would be not to participate in the research.

### 10.3 Adequacy of Protection Against Risks

#### 10.3.1 Recruitment and Informed Consent

- In brief, recruitment will only begin once the Indiana University Institutional Review Board has approved this study. All participants will be recruited from the outpatient Ryan White HIV care clinics at Eskenazi Health Hospital and Indiana University Health Methodist Hospital. Self-referrals from other venues will also be considered. The EMR filter functions (EPIC for Eskenazi Health, Cerner for Methodist Hospital) will be used to identify potentially eligible participants from the clinic databases. We will then ask each patient's primary HIV caregiver for permission to approach their patient for recruitment into the trial. If permission is granted, our dedicated trial recruiters will approach these potentially eligible patients either in person or by telephone to discuss the trial and screen for insomnia using the Insomnia Severity Index (ISI). For those with an ISI score  $\geq 11$  and who are willing to participate in the trial, the recruiters will then refer these patients to [name], the primary study coordinator, to schedule a formal Screening Visit. If eligibility is confirmed at the Screening Visit, then the purpose, procedures, and risks and benefits of the study will be discussed with the participant. Participants will have ample opportunity to ask questions and to have all concerns addressed. If the participant wishes to pursue screening, then written informed consent will be obtained (and a copy given to the participant). All consent forms will be stored in a locked file cabinet.

### 10.3.2 Protection Against Risk

10.3.2.1 Confidentiality. To minimize the risk to participant confidentiality, patient identifiers will be removed once his or her data is abstracted and recorded, and only the random study identification number (generated when consent is provided) will be used. All hardcopy study data will be kept in a secured and locked file cabinet. All electronic data will be kept in a password-protected computer database. The only link between patient identifiers and the randomized study identification number will be kept in separate files. Identifiers will never be used in the analysis or presentation of study results.

Information collected from the participant for this research may be used for future research studies or shared with other researchers for future research. If this happens, information which could identify the participant will be removed before any information are shared. Since identifying information will be removed, we cannot ask for your additional consent.

10.3.2.2 Questionnaires. Participants may feel uneasy or discomfort in completing some of the questionnaires (e.g., those assessing depressive symptoms). To minimize this risk, questionnaires will be completed in private settings, with any questions regarding completion of the questionnaires addressed by trained study team psychology personnel.

10.3.2.3 Blood draws. The risks of blood drawing will be minimized by having only experienced medical personnel perform this procedure. The amount of blood that will be drawn falls well within safety standards for blood donation.

10.3.2.4 Suicidal ideation and management. Although not an inherent risk of the study intervention or study procedures, participants may have depression as determined through completion of the PHQ-9 questionnaire. As such, these participants may have suicidal ideation at screening or develop suicidal ideation during the course of the study. We have already put into place a protection protocol for just this event in our previous studies in HIV-uninfected depressed patients (please see Appendix at end of this protocol for the full Suicide Management Plan). If a participant reports having thoughts of being better off dead or of hurting him/herself (i.e., responds with a 1, 2, or 3 to PHQ-9 Item #9 or spontaneously reports suicidal ideation), the visit will be immediately stopped, and the research assistant will interview the participant to complete the Patient Suicidality Form (see Appendix). If the participant answers “no” to all three suicide questions or if the patient answers “yes” only to Question 3 (previous attempt) and the most recent attempt was  $\geq 10$  years ago, the visit will proceed as normal, and the completed Patient Suicidality Form will be given to the principal investigator.

If the participant answers “yes” to any of the three questions (for Question #3 the previous attempt must be within the past 10 years), the research assistant will immediately contact the principal investigators. [name] (a clinical psychologist) and [name] (a physician) will review the case as soon as possible, but no later than the same day, to determine the appropriate course of action (e.g., immediately contact the patient’s primary care provider, primary HIV provider, clinical social worker, or care coordinator, consult with clinicians at Midtown Community Mental Health Center, and/or escort the patient to the Crisis Intervention Unit at Eskenazi Health). Additional authorities, including the police, may be contacted if immediate harm is of concern. Participants may be withdrawn from the study.

A letter, both an email and a hard copy version, will also be sent to the potential participant’s primary provider notifying him/her of the situation (see below).

If an enrolled participant reports having thoughts of being better off dead or of hurting him/herself during any telephone calls (e.g., a scheduling call or a call to the study team initiated by the participant), the exact same process as outlined above will be initiated. Please see the Appendix for the full Suicide Management Plan.

10.3.2.5 Adverse event financial management, grading, and reporting. In the event of an adverse event, necessary medical and professional intervention will be provided immediately and billed to the participant's medical insurance (if available). If the participant does not have insurance, care will be provided via the indigent care program at Eskenazi Health Hospital. Standard procedures for reporting deviations from protocols will be followed; serious adverse events that meet the Indiana University IRB prompt reporting requirements will be reported within 10 business days. All adverse events will be graded using The Division of AIDS Table for Grading Adult Adverse Experiences is located at: <http://roc.s-3.com/members/download/adulttox.pdf>.

10.3.2.6 Data and Safety Monitoring. Upon discussion with the NIH/National Institutes of Mental Health, this trial is considered a minimal risk study that does not require independent monitoring. As such, only Level 1 monitoring by the co-PIs (Drs. [name] and [name]) is required. The co-PIs under supervision of the IU IRB will meet every 6 months to review and ensure participant safety; monitor recruitment, accrual, randomization, retention, treatment delivery and fidelity; and review data collection and quality; suicidal ideation protection protocol triggers; any adverse events; any protocol deviations; and any IRB amendments. The IU IRB and NIH will receive copies of all monitoring reports and responses at the time of continuing review.

#### 10.4 Potential Benefits of the Proposed Research to the Participants and Others

- Potential benefits to the participants include an evaluation of their insomnia, immunology, and pro-inflammatory status. They may also derive short-term benefits from the SHUTi and sleep education/hygiene treatment programs, although this is not guaranteed. Participants will also be provided with the final trial results via their HIV providers. Finally, the participants may also benefit from knowing that their participation will accrue knowledge that could benefit other HIV-positive patients.
- Although there are no guaranteed clinical benefits from those who are randomized to treatment with SHUTi, this program appeared safe in our pilot trial involving PLW and in the thousands of HIV-negative patients in published trials. Therefore, the ancillary benefits to the participants in the proposed trial significantly outweigh the minimal risks in this study. Moreover, the proposed research may lead to other prevention and therapeutic studies that would demonstrate how to reduce inflammation in PLW, which consequently may reduce future serious non-AIDS events in the HIV-positive population. This would benefit society directly by impacting clinical practice.

#### 10.5 Importance of the Knowledge to be Gained

- The knowledge that will be gained from this study will determine the relationships between HIV, insomnia, insomnia treatment, and inflammation. This would potentially impact the clinical care of HIV-positive patients at risk for serious non-AIDS events. Furthermore, prevention and therapeutic strategies for these highly prevalent diseases can then be formulated, thereby reducing morbidity, mortality, and cost to the patients and society in general.
- The risks to the participants are considered minimal. Even if the trial results are negative, the ensuing knowledge will add substantially to our understanding on the mechanisms underlying inflammation in HIV-positive patients with insomnia. Therefore, the importance of the knowledge gained outweighs the risks to the participants.

#### 10.6 Data and Safety Monitoring Plan and Board

For this phase II trial, we have developed a Data and Safety Monitoring Plan to ensure the safety of participants and to monitor participant recruitment, accrual, randomization, and retention; treatment delivery and fidelity; and data collection and quality.

### 10.6.1 Data and Safety Monitoring Plan (DSMP)

#### 10.6.1.1 Adverse Event Monitoring.

We will systematically identify potential adverse events (AEs): (a) by conducting Eskenazi Health and IUH Health Methodist EMR searches every 6 months for all emergency department visits, outpatient visits, and hospitalizations that occurred among randomized patients and (b) by reviewing responses on a self-report questionnaire assessing for the occurrence of any potential adverse events since the last study visit/call. Any potential AEs spontaneously reported by participants will be evaluated. We will fully investigate, rate, and prepare a Case Report Form for those events that are plausibly related to insomnia, insomnia treatment, suicidal ideation, or any study procedure. For all other captured events (emergency department visits or hospitalizations typically for chronic medical conditions that are unrelated to study involvement), we will provide frequency counts for the SHUTi Intervention and Active Control study arms. We will fully investigate these events only if there is evidence of group imbalance. It is worth noting that that: (a) we are delivering safe and established insomnia interventions, (b) we are not delivering any new or experimental interventions or restricting usual care, and (c) all study procedures are noninvasive (except for the blood draw) and standard.

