To minimize treatment barriers, attrition, and subject burden, SHUTi sessions will be delivered remotely at a location selected by the participant where s/he can access a computer with internet, such as the participant's

home, the participant's work, a family member's/friend's home, or a public library. We will loan study tablet computers with data plans to patients without reliable internet access to maximize intervention update and decrease attrition. [name] laboratory and the Infectious Diseases Research Clinic at Eskenazi Health Hospital will serve as backup locations for SHUTi session delivery if a participant prefers in-person delivery.

We will deliver SHUTi with support, as it increases the efficacy of internet interventions (104-106). Specifically, the Intervention RA, a clinical psychology PhD mentee of [name], will track each participant's progress through the SHUTi dashboard and will check-in with each participant every two weeks to address any questions or issues.

We will also tell patients that, if they choose to complete SHUTi session where others are present, these other people (e.g., family member or friend) may realize that they are completing a treatment for insomnia. It will be up to each patient to decide if the available remote locations provide sufficient privacy. Up to 6 sessions will be completed by the participant between the Entry Visit and the Week 12 Study Visit at rate of a session every 1-2 weeks. No physiologic or biologic assessments will be performed during these sessions. The participants need not be fasting for these sessions.

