insomnia and provide the same list of local services. The same RA will also call each control participant every 4 weeks to assess insomnia symptoms (ISI) and will notify clinical staff to encourage additional care when indicated. Furthermore, the RA will encourage continued use of the sleep hygiene practices. Each control participant will receive usual primary care for insomnia, which in our local HIV clinics is typically limited to sleep hygiene practices (CBT-I is not offered) and use of antihistamines and trazodone (hypnotics and benzodiazepines are rarely used).

Participants randomized to either the Intervention group or the Active Control group will complete sleep diaries based on consensus sleep diary questions (108) that are incorporated into the online platforms for SHUTi and Active Control for the 14 days immediately after the Entry visit and the 14 days immediately before the Week 12 and Week 24 visits.

We will also assess treatment credibility/expectancy of benefit (109) (end of first SHUTi session or active control call) and insomnia treatment satisfaction with an item from our past trials (Week 12 Visit).

Of note, there will be no restrictions on the care that the participants can receive by their primary care providers, although we will assess changes in such care during the trial.

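### Self-reported and contact-triggered adverse events are ascertained on a different schedule or look-back in each arm, and the adverse-event questionnaire has no common timetable

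*Protocol*

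**What the plan says.** Protocol Section 10.6.1.1 names three sources of adverse events:

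- Record searches: "EMR searches every 6 months for all emergency department visits, outpatient visits, and hospitalizations that occurred among randomized patients".
- A questionnaire: "reviewing responses on a self-report questionnaire assessing for the occurrence of any potential adverse events since the last study visit/call".
- Unprompted reports: "Any potential AEs spontaneously reported by participants will be evaluated".

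Events plausibly related to insomnia, its treatment, suicidal ideation or a study procedure are each investigated and rated. For the remaining captured events, described as emergency department visits or hospitalizations, "we will provide frequency counts for the SHUTi Intervention and Active Control study arms", and "We will fully investigate these events only if there is evidence of group imbalance". Section 9.13.3 says how the emergency and hospital figures for the monitoring reports are obtained: study staff "will query the relevant EMR to extract data (type of medical visit and diagnostic codes".

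The arms have different contact schedules. In Section 5.1 the intervention research assistant "will check-in with each participant every two weeks to address any questions or issues". In Section 5.2 a different research assistant looks after control: "The same RA will also call each control participant every 4 weeks to assess insomnia symptoms (ISI"), with notification of clinical staff where indicated. Section 9.13.5 says that staff who deliver treatment are not blinded.

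The adverse-event questionnaire has no row in the Schedule of Events (Section 6.1). It is not among the instruments listed for the visits in Sections 3.3, 3.4, 3.5 and 6.2.6.7. The SAP does not mention it.

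**The concern.** A between-arm reading of adverse events needs the same opportunity to report in both arms. Here the look-back of the questionnaire is set by the most recent contact, and the spacing of contacts is part of the treatment package. Spontaneous reports also depend on how often someone from the study is in touch. In the other direction, only control has an ISI scored by telephone between visits, with a route to clinical staff, and insomnia-related events belong to the class that is always investigated and rated.

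With equal true rates, the self-reported and contact-triggered streams could therefore differ between arms, or a true difference could be masked. A reader of the by-arm data could not tell which had happened, because nothing in the plan requires an event to be labelled by how it was learned.

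**Working it through.** The documents give no adverse-event rate or count, so there is no figure of the plan's own to reproduce. The check has three parts.

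**1. Contacts.** Section 3.4 places both interventions between Entry and Week 12. At the stated intervals this gives 12/2 = 6 SHUTi check-ins and 12/4 = 3 control calls. The documents do not say when either series ends. If both run to Week 24, the numbers are 12 and 6. If check-ins stop at Week 12 and calls continue, they are 6 and 6.

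**2. Where the questionnaire is given.** There are two readings, and the arms differ under both.

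- *At contacts and visits.* The whole follow-up is covered, but the recall interval is 2 weeks in SHUTi and 4 in control while contacts last.
- *At visits only, with the stated look-back.* Suppose the last contacts before the Week 12 visit fall at Week 10 (SHUTi) and Week 8 (control). The questionnaire then asks about 2 weeks in one arm and 4 in the other.

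**3. Illustration of size.** Assume equal true event rates and exponential fading of recall with half-life h. The captured share over a look-back of L weeks is (1 − exp(−kL))/(kL), with k = ln 2/h. The half-lives are my assumption, not a figure from the documents.

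| Half-life | L = 2 | L = 4 | L = 12 |
|---|---|---|---|
| 7 days | 0.541 | 0.338 | 0.120 |
| 14 days | 0.721 | 0.541 | 0.237 |
| 28 days | 0.845 | 0.721 | 0.421 |

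For the first reading, each arm's share over 24 weeks is the mean of its two 12-week halves. A half without contacts has L = 12, because the Week 24 visit then looks back to Week 12. Example, half-life 14 days, both series ending at Week 12: SHUTi (0.721 + 0.237)/2 = 0.479; control (0.541 + 0.237)/2 = 0.389; ratio 1.23.

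For the second reading, at the Week 12 visit, the ratio is (2 × share at L = 2)/(4 × share at L = 4). At 14 days this is (2 × 0.721)/(4 × 0.541) = 0.67.

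| SHUTi-to-control capture ratio | 7 days | 14 days | 28 days |
|---|---|---|---|
| Contacts, both to Week 12 | 1.44 | 1.23 | 1.11 |
| Contacts, both to Week 24 | 1.60 | 1.33 | 1.17 |
| SHUTi to Week 24, control to Week 12 | 2.36 | 1.85 | 1.48 |
| SHUTi to Week 12, control to Week 24 | 0.98 | 0.89 | 0.88 |
| Visits only, Week 12 questionnaire | 0.80 | 0.67 | 0.59 |

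With slower fading (k = 0.02 to 0.20 per week), the first four rows give 1.01 to 1.13, 1.02 to 1.20, 1.06 to 1.55, and 0.97 to 0.87. The ratio falls on either side of 1, according to facts that the plan does not state. With the same visit timing and a look-back to the previous visit in both arms, it is 1.00 by construction.

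The record search does not use contacts, so its emergency and hospital counts do not vary with the contact schedule. Outpatient visits in the same search are less clean for a separate reason: Section 5.2 has the team urge control participants to see their HIV provider and has it notify that provider.

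**The case against.** The strongest reply is that the premise is partly inferred. No section says that adverse events are asked about at the check-ins or the control calls. Their stated purposes are questions or issues in one arm, and the ISI, staff notification and sleep hygiene in the other. A look-back is not a timetable, and both arms have other calls. Section 6.2.6.7 also refers to an appendix for the questionnaire battery, and the form might be there. All of this is fair. It does not remove the point, because the stated look-back still reaches back to contacts that are spaced differently by arm.

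Second, much capture is the same in both arms: record searches, updated diagnoses and the ISI at Weeks 12 and 24, and the requirement to document serious events and Grade 3 or 4 toxicities. This stands, and it limits the scope.

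Third, the interim information is not wholly one-sided. SHUTi participants enter diaries and insomnia symptoms into the program, and the research assistant follows a dashboard. Only the telephone ISI is specific to control, and nothing defines an ISI change as an adverse event. This also stands, although no route is stated from program entries to adverse-event review.

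A reader might infer more: that by-arm adverse-event counts in general cannot be compared, that SHUTi will be over-counted by a known factor, or that a safety conclusion for phase III will be biased. The documents do not support these readings. The promised by-arm counts and the imbalance trigger concern emergency visits and hospitalizations, drawn largely from a search that is neutral between arms. The factor rests on assumed recall and can reverse. No between-arm safety conclusion is planned: the stated aim is proof of concept and biomarker effect sizes.

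**Conclusion.** The point holds for self-reported, spontaneous and contact-triggered events. Their frequency of ascertainment or their look-back differs by arm, and no common timetable corrects this. The nominal contact ratio is 2:1 during treatment if the two intervals are followed. The effect on captured events cannot be given a size or a sign: the modelled ratios of about 0.6 to 2.4 illustrate this and are not estimates. They rest on equal true rates, exponential recall with half-lives of 7 to 28 days, and assumed contact end dates.

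The consequence is moderate. An imbalance in these events, or its absence, could not be interpreted. The emergency and hospital counts from the record search and the hsCRP endpoint are not affected, and the protocol classes the trial as minimal risk.

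**What to change.** - Add the adverse-event questionnaire to the Schedule of Events at Week 12 and Week 24 in both arms. It should be self-completed with the computer battery, identically worded, and look back to the previous study visit rather than to the previous call.
- Record the source of each event: record search, scheduled questionnaire, or spontaneous or contact-triggered.
- Report all events by arm and source. Base any between-arm comparison and the imbalance trigger on the record search and the scheduled questionnaire, and list contact-triggered events separately.
- State when the check-ins and control calls end.

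Individual review and handling of events stay as they are.

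The cost is one short form at two existing visits and one data field. There is also a real loss: a 12-week look-back captures fewer mild events. Under the 14-day half-life the modelled share is 0.24, against 0.54 to 0.72 with four- or two-week contacts. Events heard at contacts are still listed, so they drop out of the comparison but not out of the record.
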